13.5.6 Safety Analyses

Safety will be assessed by clinical review of all relevant parameters including AEs, SAEs, laboratory values, vital signs, physical exam and ECG results. Unless specified otherwise, the safety analyses will be conducted for the safety population. An interim safety analysis is planned following the completion of Cycle 1 for the first 20 patients enrolled in the Phase 2 expansion phase and will utilize a Data Safety Monitoring Board.

Summary tables and listings will be provided for all reported Treatment Emergent Adverse Events (TEAEs), defined as AEs that start on or after the first administration of study treatment. The reported AE term will be assigned a standardized preferred term using the current version of the Medical Dictionary for Regulatory Activities (MedDRA).

TEAEs will be summarized based on the number and percentage of patients experiencing the event by MedDRA system organ class (SOC) and preferred term (PT). In the event a patient

experiences repeat episodes of the same AE, then the event with the highest severity grade and strongest causal relationship to study treatment will be used for purposes of incidence tabulations.

Tabular summaries will be provided for:

- all TEAEs
- TEAEs by relationship to study treatment and maximum severity grade
- TEAEs with action of study treatment delayed/interrupted or dose reduced
- TEAEs with action of study treatment discontinued
- SAEs

For the escalation phase, the observed DLT rate in each dose cohort will be calculated by the crude proportion of patients who experienced DLT with a 2-sided 95% exact binomial CI.

All deaths that occur on study (defined as during treatment or within 30 days of treatment discontinuation) will be reported in a patient listing, which will include the primary cause of death and the number of days between the date of the last dose of study drug and death.

Hematology and serum chemistries will be summarized in a descriptive manner by calculating the mean, standard deviation, median, and range as follows:

- baseline value
- minimum post baseline value
- maximum post baseline value
- average post baseline value
- last post baseline value

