5.2 Sample Size

5.2.1 Phase 1b Dose Determination Phase

Three to six patients will be enrolled in each dose cohort based on a standard Phase 1 dose-finding scheme.

A starting sample size of 3 evaluable patients per dose cohort, expanding to 6 in the event of a marginal DLT rate (33%) was deemed to be a safe and conventional approach in dose-finding. Assuming a true DLT rate of 5% or less, there would be a 3% chance that dose escalation would be halted in a given cohort (i.e. observing 2 or more patients with DLT). If a true DLT rate of 50% is assumed, then there would be an 83% chance that dose escalation would be halted in a given cohort.

6 patients will need to be treated in a dose level for it to be considered as MTD or RP2D.

**Statistical Analysis Plan
SNDX-275-0602 (TRIO025)
DM-025-037**

Patients who discontinued the study for reasons other than study drug related toxicities before completing Cycle 1 will be replaced.

Therefore, between 6 and 18 patients will be included in the Dose Determination Phase.

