6.7 Dose-limiting Toxicity (DLT)

DLT is defined as the occurrence of specific events defined in Section 9.6 of the protocol within the first cycle of treatment (i.e. between Day 1 to Day 21 of Cycle 1) of entinostat in combination with atezolizumab that are considered by the investigator to be at least possibly related to study drug using the National Cancer Institute (NCI) Common Terminology Criteria for Adverse Events (CTCAE) version 4.03.

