7.3 Safety Analysis Set

The **Safety Analysis Set** consists of all patients who receive any study treatment, and will be used for the analysis of safety data in both Phase 1b and Phase 2 portions of the study. This population will be based on the first dose received at cycle 1, if this differs from that to which the subject was randomized and will be used for the analysis of safety data. This population set will be identified using the SAFFL (Safety Population Flag) as defined in ADSL according to ADaM.

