10.9 Safety Analyses

Safety analyses will be performed on the safety analysis set.

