10.9.2 Adverse Events

The reported AE term will be coded using the current version of the MedDRA. The severity of AE will be presented as reported by the investigator based on NCI CTCAE version 4.03.

Incidence of TEAE will be tabulated by SOC, PT for:

- All TEAEs
- TEAEs by relationship to study treatment and maximum severity grade
- TEAEs with action of study treatment delayed/interrupted or dose reduced
- TEAEs with action of study treatment discontinued
- Serious Adverse Events (SAE) (not Serious TEAEs)

In the event a patient experiences repeat episodes of the same AE, the event with the highest severity grade and strongest causal relationship to study treatment will be used for purposes of incidence tabulations.

All AEs leading to deaths will be summarized (not TEAEs). An AE will be considered as leading to death if it has a grade 5.

Detailed listings for all AEs will be provided. A flag will be used to identify which AE is considered as treatment emergent.

For the Phase 1b dose determination phase, the observed DLT rate in each dose cohort will be calculated by the crude proportion of patients who experienced DLT with a 2-sided 95% exact binomial CI.

**Statistical Analysis Plan
SNDX-275-0602 (TRIO025)
DM-025-037**

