Title	Population	Description
		and the corresponding DLT at cycle 1 and 2 for each treatment group. For Phase 1b only.
Progression-Free Survival	FAS ¹	Summary of PFS results including treatment comparison results. Separate tables will be done for PFS based on RECIST 1.1 and irRECIST.
Progression-Free Survival	FAS ¹	Summary of PFS results including treatment comparison results (sensitivity analysis). Separate tables will be done for PFS based on RECIST 1.1 and irRECIST.
Objective Response Rate	FAS ¹	Summary of ORR results including treatment comparison results. Separate tables will be done for ORR based on RECIST 1.1 and irRECIST.
Clinical Benefit Rate	FAS ¹	Summary of CBR results including treatment comparison results. Separate tables will be done for CBR done based on RECIST 1.1 and irRECIST.
Overall Survival	FAS ¹	Summary of OS results by treatment group.
Duration of Response (those with CR/PR or irCR/irPR)	FAS ¹	Summary of DOR results by treatment group.
Time to Response (same comment as above)	FAS ¹	Summary of TTR results by treatment group.
TEAEs Overview	Safety	Tabulates the number of patients with TEAEs, Related TEAEs, Grade 3 / 4 TEAEs, TEAEs with action taken as dose reduced or drug interrupted, TEAEs leading to drug withdrawn, SAE, Fatal AE. For Phase 1b, the DLT rate will be presented.

**Statistical Analysis Plan
SNDX-275-0602 (TRIO025)
DM-025-037**

Title	Population	Description
TEAEs	Safety	Summary by SOC and PT for each treatment group.
TEAEs	Safety	Summary by PT for each treatment group ordered by frequency.
TEAEs per Maximum Grade	Safety	Summary by SOC and PT for each treatment group.
TEAEs Related to Entinostat	Safety	Summary by SOC and PT for each treatment group.
TEAEs Related to Entinostat per Maximum Grade	Safety	Summary by SOC and PT for each treatment group.
Grade 3 / 4 TEAEs	Safety	Summary by SOC and PT for each treatment group.
Grade 3 / 4 TEAEs	Safety	Summary by PT for each treatment group ordered by frequency.
TEAEs Related to Atezolizumab	Safety	Summary by SOC and PT for each treatment group.
TEAEs Related to Atezolizumab per Maximum Grade	Safety	Summary by SOC and PT for each treatment group.
TEAEs Related to Entinostat and/or Atezolizumab	Safety	Summary by SOC and PT for each treatment group.
TEAEs Related to Entinostat and/or Atezolizumab per Maximum Grade	Safety	Summary by SOC and PT for each treatment group.

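### The Phase 1b DLT rate is reported on all treated patients rather than DLT-evaluable patients, and the DLT window that defines its numerator is stated inconsistently

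*SAP*

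**What the plan says.** **Estimator.** In SAP 10.9.2, "the observed DLT rate in each dose cohort will be calculated by the crude proportion of patients who experienced DLT", with a two-sided 95% exact binomial interval. The sentence names no denominator.

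**Population.** The parent section, SAP 10.9, supplies one: "Safety analyses will be performed on the safety analysis set". SAP 7.3 says that set "consists of all patients who receive any study treatment". In SAP 11.1 the Dose Limiting Toxicity table and the TEAEs Overview both list Safety as their population, and the Overview adds "For Phase 1b, the DLT rate will be presented". Protocol 13.5.6 has the same default: "Unless specified otherwise, the safety analyses will be conducted for the safety population". The protocol synopsis agrees. SAP section 7 contains only the Full Analysis, Per-protocol and Safety sets.

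**Evaluability and replacement.** Protocol 9.6 and 13.3 define a DLT-evaluable patient: one with a DLT in Cycle 1, or one who received all Cycle 1 doses of both drugs without a DLT. Protocol 9.6 allows non-evaluable patients to be replaced. SAP 5.2.1 says that patients who leave before completing Cycle 1 for reasons other than drug toxicity will be replaced, and it sizes cohorts on evaluable patients: "A starting sample size of 3 evaluable patients per dose cohort".

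**Window.** SAP 6.7 restricts DLTs to events "within the first cycle of treatment (i.e. between Day 1 to Day 21 of Cycle 1". The planned DLT table reports patients with DLTs "and the corresponding DLT at cycle 1 and 2 for each treatment group. For Phase 1b only". Protocol 9.6 sets a window from C1D1 to C2D1, then adds that being unable to receive more than 60% of the planned entinostat over two cycles is also a DLT.

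**The concern.** The 3+3 design counts evaluable patients and replaces those who are not evaluable. The summary of the same data counts everyone treated. By definition a non-evaluable patient has no Cycle 1 DLT, so for Cycle 1 DLTs she can add only to the denominator and the shift is always downward.

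Protocol 13.4 assesses the recommended dose by DLT incidence and overall tolerance, and this rate with its exact interval is the planned numerical summary of that incidence for each dose cohort. As written, it would not describe the patients on whom the dose decision was made. Separately, the SAP's definition and its table give different answers on whether a DLT under the two-cycle criterion counts, so the numerator is not uniquely defined even when nobody is replaced.

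**Working it through.** **1. The plan's own figures.** Protocol 13.1.1 and SAP 5.2.1 state a 3% and an 83% chance of halting at true DLT rates of 5% and 50%. Under the 3+3 rule a cohort is not halted with 0 DLTs in the first 3 patients, or with 1 in the first 3 and 0 in the next 3:

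P(halt) = 1 − [(1−p)³ + 3p(1−p)²(1−p)³]

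- p = 0.05: 2.66%
- p = 0.50: 82.81%

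Both match the plan. A fixed cohort of six gives 3.28% and 89.06%, and the second does not match. The stated figures therefore rest on 3+3 cohorts in which every counted patient is evaluable.

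**2. Effect of the denominator.** The inputs are six evaluable patients (the size required to declare an MTD or RP2D) and the Clopper-Pearson 95% interval named in the plan. The documents do not give the number of treated, non-evaluable, replaced patients per cohort, so 0, 1 or 2 is assumed.

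| DLTs | 0 replaced (n = 6) | 1 replaced (n = 7) | 2 replaced (n = 8) |
|---|---|---|---|
| 0 | 0% (0–45.9) | 0% (0–41.0) | 0% (0–36.9) |
| 1 | 16.7% (0.4–64.1) | 14.3% (0.4–57.9) | 12.5% (0.3–52.7) |
| 2 | 33.3% (4.3–77.7) | 28.6% (3.7–71.0) | 25.0% (3.2–65.1) |

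The first column is the evaluable-patient result; the others are what the Safety set would report. In the last row, a cohort that fails the rule of fewer than 33% of 6 would be reported with a rate below 33%.

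**3. The window.** Three entinostat doses per cycle make six over two cycles. More than 60% requires at least 4 of 6 (66.7%), since 3 of 6 is 50%.

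- *Patient evaluable in Cycle 1.* She takes all three Cycle 1 doses and none in Cycle 2: 3/6 = 50%. If this counts as inability, she is a DLT under protocol 9.6 and in the planned table, but not under SAP 6.7. With one other DLT among the six, the rate is 1/6 = 16.7% or 2/6 = 33.3%, depending on the passage followed.
- *Patient not evaluable in Cycle 1.* She misses one Cycle 1 dose for a non-drug reason and takes one of three in Cycle 2: (2 + 1)/6 = 50%. She may meet the two-cycle criterion, but protocol 13.3 judges evaluability on Cycle 1 alone. With 1 DLT in 6 evaluable patients, leaving her out gives 1/6 = 16.7%, and counting her in both numerator and denominator gives 2/7 = 28.6%. No text says which.

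**The case against.** **The effect is conditional and small.** It needs a patient who was dosed, not evaluable and replaced; someone replaced before any dose is outside the Safety set. One replacement moves 16.7% to 14.3%, which is slight against an interval of 0.4% to 64.1%. The dose decision uses fewer than 2 of 6, at least 2 DLTs, or fewer than 33% of 6, and the denominator does not touch it. All of this stands and limits the weight of the point. It does not make the stated denominator right.

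**The DLT sentence names no denominator.** It refers to each dose cohort, and cohorts are sized on evaluable patients. That reading would be available if the SAP stopped there, but SAP 10.9 and the population column of both tables say Safety. It is true that the Dose Limiting Toxicity row describes counts, which replacement does not change; only the TEAEs Overview row mentions a rate.

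**The window conflict is narrow.** SAP 6.7 refers to protocol 9.6 for its events, and 9.6 itself says the dose over two cycles must be evaluated as one of the DLT criteria, so a two-cycle table is consistent with the protocol. This is fair, but it leaves the Day 1 to Day 21 limit in SAP 6.7 in conflict with both.

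**The second two-cycle example is unusual.** Protocol 9.6 also lists inability to receive all three Cycle 1 entinostat doses, printed at the end of the list of exceptions. If that is a DLT criterion, some patients with missed doses become DLTs and so are evaluable, and fewer patients are left in the gap. The gap is secondary, but that item's status also needs to be made clear.

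**An evaluable set brings its own membership question.** The Safety set leaves no doubt that the second example patient belongs in the denominator. This is correct, and it is why the new set needs an explicit rule for her.

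**Conclusion.** The point holds. Followed as written, the SAP divides Phase 1b DLTs by all treated patients, and every treated, non-evaluable, replaced patient lowers the reported rate and its upper limit. If one or two replacements are assumed, 1 DLT in 6 loses 2.4 or 4.2 percentage points (16.7 − 14.3; 16.7 − 12.5), and its upper limit loses 6.2 or 11.4 (64.1 − 57.9; 64.1 − 52.7). With no such patient the two denominators agree. The protocol shares the default in 13.5.6 and the synopsis, so the SAP does not depart from it and both documents need correcting.

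The numerator inconsistency does not depend on replacement. It exists wherever the two-cycle criterion comes into play.

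This should be corrected before the Phase 1b tables are produced. It concerns whether the reported summary describes the patients behind the dose decision; it is not a flaw in the dose-finding rule.

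**What to change.** 1. Add a DLT-evaluable set to SAP section 7, using the definition in protocol 9.6 and 13.3.
2. Name it as the denominator for the DLT rate and its exact interval in SAP 10.9.2, for the Dose Limiting Toxicity table, and for the DLT line of the TEAEs Overview. Add matching wording to protocol 13.5.6 and the synopsis. The other adverse event tables stay on the Safety set, so no toxicity information is lost.
3. Reconcile SAP 6.7, SAP 11.1 and protocol 9.6 so that one window and one list of criteria define the numerator. Which criteria and window apply is for the sponsor to settle.
4. State whether a patient who is not evaluable in Cycle 1 but later meets the two-cycle criterion enters both numerator and denominator or is only listed.

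The cost is SAP wording, one analysis flag derived from dosing and adverse event data already collected, the counting rule in item 4, and a short alignment of the protocol. No new data and no design change are needed.

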10.9.3 Death

All deaths will be reported in a patient listing, which will include the primary cause of death, and the number of days between the date of last dose to study drug and death.

10.9.4 Laboratory Values

Hematology and serum blood chemistry will be summarized in descriptive statistics by calculating the mean, standard deviation, median, and range for the following:

- Baseline value
- Minimum post baseline value
- Maximum post baseline value
- Average post baseline value
- Last post baseline value

Laboratory values will be assigned toxicity grade when available using NCI CTCAE version 4.03. Shift tables in laboratory toxicity grades (comparing baseline grade with worst post-baseline grade) will be analyzed using standard shift tables, presenting number and proportion of patients and their maximum grade shift.

For laboratory tests without a toxicity grading scale, the shift table will present directional shifts from baseline to above or below the laboratory standard normal range using the maximum increase and/or decrease observed throughout the course of treatment/observation.

10.9.5 ECOG Performance Status

Tabulation of ECOG Performance Status results will be done for the following:

- Baseline value
- Minimum post baseline value
- Maximum post baseline value
- Last post baseline value

A shift table will be provided as well from baseline status to the worst status of post-baseline time points.

**Statistical Analysis Plan
SNDX-275-0602 (TRIO025)
DM-025-037**

10.9.6 Vital Signs

Vital sign measurements will be summarized by descriptive statistics in the same manner described for laboratory values.

10.9.7 Electrocardiogram (ECG)

ECG results will be tabulated in terms of frequency and percentage of patients according to findings reported by investigators at the assessed time points.

10.9.8 Concomitant Medication

Prior and concomitant medications are coded to the current version of World Health Organization Drug Dictionary (WHODD). The generic term will be tabulated and listed by patient.

10.10 Subgroup Analysis

Subgroup analyses will be done for PFS and OS to assess internal consistency of study results and whether there is significant treatment heterogeneity across any of the subgroups. Tests within each subgroup and tests for subgroup-by-treatment-interaction terms will use an unstratified test from an unstratified Cox proportional hazards model. Additionally, these subgroup analyses will also be performed using a stratified test/model.

The following subgroup analyses are planned:

Table 3 – Planned Subgroup Analyses

Subgroup	Reason
Geographical region (US vs. Rest of World)	IWRS stratification factor
Prior endocrine therapy	Baseline demographic or prognostic factor
Prior chemotherapy	Baseline demographic or prognostic factor
Prior adjuvant/neoadjuvant systemic anticancer therapy	Baseline demographic or prognostic factor
ECOG 0 vs. ECOG 1	Baseline demographic or prognostic factor
Disease stage at study entry: unresectable locally recurrent vs. metastatic	Baseline demographic or prognostic factor
Number of metastatic sites: ≥ 3 vs. < 3 (based on the location/organ; i.e. 3 liver lesions count)	Baseline demographic or prognostic factor

**Statistical Analysis Plan
SNDX-275-0602 (TRIO025)
DM-025-037**

as 1 metastatic site)	
Disease-free interval: none, < 24 months, vs. > 24months (based on the first surgery expected to be curative, to the first relapse/progression date)	Baseline demographic or prognostic factor

10.11 Pharmacokinetic and Antidrug Antibody Analyses –

It will be done in a separate document.

10.12 Correlative Analyses

It will be done in a separate document.

11. LIST OF PLANNED TABLES, FIGURES, LISTINGS

11.1 Planned Tables

Title	Population	Description
Patient Disposition	FAS	Tabulates the disposition of all patients by treatment group, including the number of patients in each population set as well as the number of patients discontinued from study treatment, and the number of patients discontinued from study. The reason for drug discontinuation and study discontinuation will also be summarized.
Stratification Factors	FAS	Tabulates the stratification factor (Geographic Location – US vs. Rest of World) by treatment group. (Phase 2 only.)
Protocol Deviations	FAS	Tabulate the number of patients who reported protocol deviations by deviation category for each treatment group.
Eligibility Deviations	FAS	Tabulates the number of patients who violates inclusion/exclusion criteria by criterion for each

**Statistical Analysis Plan
SNDX-275-0602 (TRIO025)
DM-025-037**

Title	Population	Description
		treatment group
Baseline Demographics	FAS	Tabulates summary statistics of the demographics (age, race, ethnicity, menopausal status, weight, height and ECOG status at baseline).
Disease Characteristics	FAS and Safety	Tabulates summary statistics for time from initial diagnosis to randomization, primary tumor location, staging at initial diagnosis, histopathological type at initial diagnosis, histopathological grade at initial diagnosis, disease status at registration, time from metastatic/locally recurrent disease to randomization, hormonal receptor status, and HER2 status.
Prior Surgery for Breast Cancer	FAS	Tabulates the number of patients with type and location of surgery for each treatment group.
Prior Systemic Anti-Cancer Therapy	FAS	Tabulates the number of patients by type and indication of the systemic cancer therapy for each treatment group.
Prior Radiation Therapy	FAS	Tabulates the number of patients by site and indication of prior radiation therapy for each treatment group.
Medical History	FAS	Summarizes medical history by SOC and PT for each treatment group.
Study Drug Exposure	Safety	Summarizes the number of cycles, the duration of treatment, cumulative dose, and RDI by treatment group. The number of dose interruptions/discontinuation or reduction will also be summarized.
Compliance	Safety	Compliance assessment will be summarized by each visit.
Dose Limiting Toxicity	Safety	Tabulates the number of patients experienced DLT

**Statistical Analysis Plan
SNDX-275-0602 (TRIO025)
DM-025-037**

Title	Population	Description
		and the corresponding DLT at cycle 1 and 2 for each treatment group. For Phase 1b only.
Progression-Free Survival	FAS ¹	Summary of PFS results including treatment comparison results. Separate tables will be done for PFS based on RECIST 1.1 and irRECIST.
Progression-Free Survival	FAS ¹	Summary of PFS results including treatment comparison results (sensitivity analysis). Separate tables will be done for PFS based on RECIST 1.1 and irRECIST.
Objective Response Rate	FAS ¹	Summary of ORR results including treatment comparison results. Separate tables will be done for ORR based on RECIST 1.1 and irRECIST.
Clinical Benefit Rate	FAS ¹	Summary of CBR results including treatment comparison results. Separate tables will be done for CBR done based on RECIST 1.1 and irRECIST.
Overall Survival	FAS ¹	Summary of OS results by treatment group.
Duration of Response (those with CR/PR or irCR/irPR)	FAS ¹	Summary of DOR results by treatment group.
Time to Response (same comment as above)	FAS ¹	Summary of TTR results by treatment group.
TEAEs Overview	Safety	Tabulates the number of patients with TEAEs, Related TEAEs, Grade 3 / 4 TEAEs, TEAEs with action taken as dose reduced or drug interrupted, TEAEs leading to drug withdrawn, SAE, Fatal AE. For Phase 1b, the DLT rate will be presented.

**Statistical Analysis Plan
SNDX-275-0602 (TRIO025)
DM-025-037**

Title	Population	Description
TEAEs	Safety	Summary by SOC and PT for each treatment group.
TEAEs	Safety	Summary by PT for each treatment group ordered by frequency.
TEAEs per Maximum Grade	Safety	Summary by SOC and PT for each treatment group.
TEAEs Related to Entinostat	Safety	Summary by SOC and PT for each treatment group.
TEAEs Related to Entinostat per Maximum Grade	Safety	Summary by SOC and PT for each treatment group.
Grade 3 / 4 TEAEs	Safety	Summary by SOC and PT for each treatment group.
Grade 3 / 4 TEAEs	Safety	Summary by PT for each treatment group ordered by frequency.
TEAEs Related to Atezolizumab	Safety	Summary by SOC and PT for each treatment group.
TEAEs Related to Atezolizumab per Maximum Grade	Safety	Summary by SOC and PT for each treatment group.
TEAEs Related to Entinostat and/or Atezolizumab	Safety	Summary by SOC and PT for each treatment group.
TEAEs Related to Entinostat and/or Atezolizumab per Maximum Grade	Safety	Summary by SOC and PT for each treatment group.
TEAEs with Action Taken as Treatment delayed/interrupted for Entinostat	Safety	Summary by SOC and PT for each treatment group.
TEAEs with Action Taken as Treatment delayed/interrupted for Atezolizumab	Safety	Summary by SOC and PT for each treatment group.
TEAEs with Action Taken as Dose Reduced	Safety	Summary by SOC and PT for each treatment group. (For Phase 2 only)

**Statistical Analysis Plan
SNDX-275-0602 (TRIO025)
DM-025-037**

Title	Population	Description
for Entinostat		
TEAEs Leading to Treatment Discontinuation	Safety	Summary by SOC and PT for each treatment group.
TEAEs Leading to Treatment Discontinuation	Safety	Summary by PT for each treatment group ordered by frequency.
SAE	Safety	Summary by SOC and PT for each treatment group.
AEs Leading to Death	Safety	Summary by SOC and PT for each treatment group.
Laboratory Values	Safety	Summary of each laboratory parameter at baseline, minimum post baseline value, maximum post baseline value, average post baseline value and last post baseline value for each treatment group. In addition, shift tables will be presented.
ECOG Performance Status	Safety	Summary of ECOG performance status at each baseline, minimum post baseline value, maximum post baseline value, last post baseline value for each treatment group. In addition, a shift table will be presented.
Vital Signs	Safety	Summary of descriptive statistics for each vital sign measurements will be done for baseline value, minimum post baseline value, maximum post baseline value, average post baseline value, and last post baseline value for each treatment group.
ECG	Safety	Tabulate the frequency and percentage of patients according to findings reported at each time point for each treatment group.
Prior and Concomitant Medications	Safety	Tabulate the frequency and percentage of patients according to generic name. Summary will be presented separately for prior medications and

**Statistical Analysis Plan
SNDX-275-0602 (TRIO025)
DM-025-037**

Title	Population	Description
		concomitant medications.
Anticancer Therapy Received after end of study treatment	FAS	Tabulate the frequency and percentage of patients according to type of anticancer therapy received after end of study treatment.

¹ Separate tables to be produced based on per-protocol analysis set if needed.

